2. STUDY DESIGN

An analytical, longitudinal, experimental, prospective, controlled and randomized clinical study will be conducted to analyze the cause-effect relationship of the Müller & Puig physiotherapy protocol under study in relation to the change in pain, functionality (modified Harris scale) and the range of mobility (ROM) in subjects surgically operated by Femoro-acetabular Impingement (FAI) by arthroscopy.

The study will be simple blind with blinded evaluator strategy with two parallel groups. The surgeons (recruitment) and assessors will be blinded with respect to the group belonging to the subject. The statistician will be blinded to the subjects group until the statistical analysis is completed. It is not possible to blind the physiotherapist who executes the treatment protocol or the study subjects. Subjects will be asked not to disclose their membership group or consult with the surgeon or the evaluator.

The randomization approach will be prepared by means of a randomization computer program, attributing a 1:1 ratio to the membership group. The interventionist physiotherapist will perform the randomization on the day of the first post-surgery physiotherapy session.

All participants will be informed of the purpose of the study through an information document prepared for this purpose and will be clarified any doubts that may arise. After answering as many questions as necessary, the subject must sign the informed consent document to be part of the study. The principles of the Declaration of Helsinki (2004) will

be respected at all times. The data collected will be treated confidentially by applying the current legislation on the protection of personal data (Organic Law 15/1999 of December 13, Protection of Personal Data) and / or any other applicable.

This study has been admitted by the Research and Ethics Committee of General University Hospital of Elche PI 6/2019.

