The statistical program that we will use will be SPSS v.20. To determine the sample size, a pilot study will be conducted with the same methodology as the original study to a group of 10 subjects. These subjects will be assigned to the same group. This pilot study will provide us with the estimates of the mean and variance of the response variable, thus being able to calculate the appropriate sample size by determining a minimum power value of 80% ($W > 80\%$) and a confidence level of 95% ($p < 0.05$).

The pilot sample will be part of the final sample to be studied if there are no changes in the protocol or in the variables to be measured.

The FAI is an important cause of coxarthrosis. Hip osteoarthritis is a pathology of high prevalence, with important socioeconomic repercussions. In Spain, 16% of the population over 20 years of age suffers, with a clear prevalence in women.

In a retrospective radiological study, Marín et al found around 70% the presence, on radiographs performed years before the intervention, of femoral and acetabular signs suggestive of femoroacetabular shock in children under 55 years who underwent total arthroplasty of hip. Other authors have reported values around 45% in patients pending intervention of hip prostheses with an age range between 30 and 82 years.

We consider it feasible to obtain a sample necessary for the present study (around 30 subjects per group) in view of the sample size of published articles on the effectiveness of conservative or postoperative treatment protocols for hip disorders and FAI and the high prevalence of FAI. The estimated time of obtaining the necessary sample will be around 6 months.

Descriptive analysis: A descriptive statistical analysis of all the variables will be carried out using frequency tables for the qualitative variables, and the minimum, maximum, average and standard deviation for the quantitative variables.

Inferential analysis: In relation to the inferential analysis, the statistical tests described below will be performed.

- a. Normal distribution test of Kolmogorov-Smirnov to identify the distribution of the samples.
- b. Levene test to check if the variances are homogeneous.

- c. ANOVA test (when the sample were are normal) or Kruskal-Wallis test (when it do not comply with normality) to check the homogeneity of the characteristics of the subjects between the different groups before the intervention.

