- d. For the comparison of means between the results of both groups we will use the t-Student test of related samples and one-way ANOVA (when they are normal) or Mann-Whitney U test or Wilcoxon W test (when they do not meet the normal).
- e. Chi square test or ANCOVA to analyze the influence of the general characteristics of the sample on the effect of the intervention.
- f. For the reliability analysis of the measuring tools, Cronbach's alpha test will be used.
- g. Regression analysis using the multiple linear model to study the relationship between sets of variables.

A significance index of $p < 0.05$ will be established.

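### The 80% power target is tied to no between-arm difference: the one-group pilot can supply an SD but not the effect, and the plan states none

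*Combined protocol and SAP*

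**What the plan says.** The design is a randomized comparison with 1:1 allocation and a "blinded evaluator strategy with two parallel groups" (protocol, section 2). Section 4 says that the intervention results will be compared with those of the control group. Measurements are taken before surgery and at 4 and 14 weeks after it (section 7).

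The SAP, under Size Sample and Feasibility, gives one route to the sample size:

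- The source is a pilot: "a pilot study will be conducted with the same methodology as the original study to a group of 10 subjects".
- On allocation in the pilot: "These subjects will be assigned to the same group".
- On what the pilot is for: "This pilot study will provide us with the estimates of the mean and variance of the response variable". The size is then to follow "by determining a minimum power value of 80" per cent and "a confidence level of 95" per cent.

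The pilot subjects join the final sample if neither the protocol nor the variables change. Later in the same section, a feasibility sentence expects "around 30 subjects per group) in view of the sample size of published articles" and also cites the prevalence of the condition.

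No target difference, minimum important difference or external effect estimate appears in either part of the document. The response variable is referred to in the singular but not named. Section 5.2 lists eleven dependent measures: six ranges of motion, three orthopedic tests, VAS and the modified Harris scale.

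**The concern.** The size of a two-arm trial with a continuous outcome depends on the significance level, the power, the SD and the difference between arms to be detected. The SAP gives the first two and a source for the third. For the fourth it offers only the pilot mean, which is either one group's level or that group's change over time. Neither is a difference between the intervention and the control protocol. Knowing the pilot SD exactly would not help, so this point is separate from the imprecision of an estimate from 10 people.

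Until a difference is named, a statement of 80% power has no content, and readers cannot tell which effects the trial could reliably detect or miss. There is also a practical hazard. The only effect that a one-group pilot can yield is a change over time, and every change from baseline here spans the arthroscopy, which both arms receive. If that change were entered as the effect, the resulting size would be too small for a comparison of two rehabilitation protocols.

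**Working it through.** **Inputs from the documents.** Significance level 0.05; power at least 80%; allocation 1:1; about 30 per group; one group in the pilot.

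**Not in the documents, so assumed.** Two-sided testing (the SAP does not state sidedness); an independent two-sample t test; standardized differences d = (difference between arms)/SD, shown over a range.

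**Step 1. Can the plan's own figure be reproduced?** The usual approximation is n per arm = 2(1.96 + 0.84)²/d². No difference and no SD are given, so d is unknown and 30 per group cannot be reproduced. It can only be solved backwards.

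**Step 2. What does 30 per arm detect?** In the normal approximation, d = (1.960 + 0.842) × √(2/30) = 0.72. The exact t calculation uses 58 degrees of freedom, critical value 2.002 and noncentrality d√(30/2) = 3.873d. Setting power to 0.80 gives d = 0.736, or 0.74 SD.

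**Step 3. Power at 30 per arm for smaller differences (noncentral t).**

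| Assumed d | Noncentrality | Power at 30 per arm | n per arm for 80% |
|---|---|---|---|
| 0.3 | 1.162 | 21% | 176 |
| 0.5 | 1.936 | 48% | 64 |
| 0.74 | 2.849 (at d = 0.736) | 80% | 30 |

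The same 30 per arm therefore gives anything from 21% to 80% power over this range, depending on a difference that the plan does not state.

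**Step 4. A hypothetical: the pilot's pre-post change is entered as the between-arm difference.** Assume that change is 1.0 SD.

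- Size returned: 16 per arm gives 78.1% power and 17 per arm gives 80.7%, so the formula returns 17 per arm.
- Actual power with 17 per arm if the true between-arm difference is 0.5 SD (assumed): 32 degrees of freedom, noncentrality 0.5 × √(17/2) = 1.458, critical value 2.037, power 29%.

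The normal approximation differs from the exact t sizes by one per arm: 16 rather than 17, 63 rather than 64, and 175 rather than 176.

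**The case against.** The strongest reply is that the SAP never says the pilot mean, or a pre-post change, will be used as the effect. It can be read as taking the SD and a reference level from the pilot, with the difference set separately when the size is calculated. A one-group pilot is a legitimate source for an SD. In addition, the 80% is a target for a calculation still to be done, so no completed power claim exists to be wrong. The sentence about 30 per group may justify feasibility rather than derive the size.

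Much of this stands. A reader might infer that the trial will be sized on the change from before surgery, perhaps because the SAP's inferential analysis (item d) lists a related-samples t test for comparing the groups. The documents do not support that inference, so step 4 is only a hypothetical. Larger assumed changes would give still smaller sizes: 9 per arm at 1.5 SD and 6 at 2.0 SD. These fit poorly with a 10-subject pilot group that may be kept and with about 30 expected per group, so no weight is placed on them. Nor do the documents say how a non-significant result would be interpreted.

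The reply does not remove the gap. The SAP names the pilot mean and variance as what makes the calculation possible. Even if the pilot is for the SD only, no target difference is given and no method for choosing one. Reading the 30 per group as pure feasibility confirms that it is not linked to the power target.

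**Conclusion.** The point holds. The stated method cannot produce a sample size for the two-arm comparison, because its only empirical source contains one group and nothing else in the documents supplies a between-arm difference. The 80% target therefore refers to no effect of intervention versus control, and about 30 per group is not linked to it.

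At 30 per arm, 80% power requires a difference of 0.74 SD; smaller differences have materially less, as the table shows. These figures rest on a two-sided 5% t test with 30 analysed per arm. The 0.3 and 0.5 SD differences are assumptions and do not estimate the true effect. Whether 30 per arm is too few cannot be judged until the sponsor states the difference that matters. The finding is that the size is unsupported, not that it has been shown to be wrong. It should be corrected before the sample size is fixed.

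**What to change.** In the SAP, under Size Sample and Feasibility:

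1. Name one response variable, assessed at 14 weeks, as the basis for the sample size.
2. State a prespecified minimum important difference between arms in that variable, with its justification, and base the size on it.
3. Say that the pilot supplies the SD only and that its mean is not used as the effect.
4. Name the test behind the calculation and state that it is two-sided.
5. Beside the figure of about 30 per group, state what that size delivers with a two-sided 5% two-sample t test: 80% power for 0.74 SD, 48% for 0.5 SD and 21% for 0.3 SD.

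The cost is a few sentences and a less favourable power statement. No extra patients are needed if 30 per arm is kept and its limits are stated. In that case, if the chosen difference is below 0.74 SD, the plan must give the lower power rather than 80%. Keeping 80% for a smaller difference means more patients, for example 64 per arm at 0.5 SD.

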B. Pre-surgery evaluation: the Harris scale questionnaire modified prior to the surgical procedure will be completed. After signing the informed consent, the pre-surgical measurement will be carried out following the following sequence:

- Assessment tests of abduction, adduction, flexion, extension, internal rotation and external rotation ROM of the hip
- Next, the Ober, Fabere and Faddir muscle tests will be performed.
- Finally, the pain will be evaluated through the Visual Analog Scale (VAS)

C. Randomization: After the presurgical evaluation and following a simple randomization process by means of a computer program, the subjects are assigned to the control or intervention group.

D. Hip arthroscopy: The study subjects will receive adequate pre- and postoperative care including health education and exercise plan for the immediate postoperative period, in addition to a follow-up visit by the traumatologist after two weeks of the intervention.

E. Intervention: The subjects of the control group follow the general postsurgical treatment protocol described by Gocen et al. The subjects of the intervention group will perform a physiotherapy session of 45 minutes each one every two weeks for a total of 7 sessions (weeks 2, 4, 6, 8, 10, 12 and 14 post surgery) following the protocol described. In addition, they will have to follow a physiotherapy exercise plan at home whose compliance they will have to register in an activity diary to check adherence to treatment.

F. Post-surgery evaluation 1: The evaluation described in section B and C is repeated 4 weeks after surgery to subjects of both groups.

G. Post-surgery evaluation 2: The evaluation described in section B and C is repeated after 14 weeks of the surgery for the subjects of both groups, and the individual study is finished.

In both groups, it will be advised to avoid stairs, ramps, squats, forced hip flexion and legs crossing in all phases. The subjects that develop a deterioration in the Modified Harris scale or in the VAS at 4 weeks after surgery compared with the pre-surgical data or those subjects that reflect complications of the surgery will be evaluated again by their corresponding traumatologist to decide whether or not to remain in the program. All complications will be documented by the principal investigator. No adverse effects are expected.

Statistical Analysis Plan (SAP)

Size Sample and Feasibility

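### The 10 pilot subjects all go to one group and then count in the final sample, so up to about a third of one arm of a 1:1 randomised trial would not be randomised

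*Combined protocol and SAP*

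**What the plan says.** The SAP, under Size Sample and Feasibility, states that "a pilot study will be conducted with the same methodology as the original study to a group of 10 subjects". It continues: "These subjects will be assigned to the same group". The group is not named. The purpose is given as "This pilot study will provide us with the estimates of the mean and variance of the response variable", from which a sample size with at least 80% power at the 5% level is to be calculated. The response variable is not named either. Retention is the default: "The pilot sample will be part of the final sample to be studied if there are no changes in the protocol" or in the variables measured. The same section considers a sample of "around 30 subjects per group" feasible, with recruitment over about 6 months.

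Protocol section 2 (Study design) describes a randomised controlled study, "attributing a 1:1 ratio to the membership group". Section 8 (Study sequence), step C, assigns subjects to control or intervention "following a simple randomization process by means of a computer program". The inferential analysis in the SAP has no exclusion, no term for pilot status and no sensitivity analysis without the pilot subjects.

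**The concern.** A subject placed in a predetermined group has not been randomised. The cause-effect aim in protocol section 2 rests on the randomised comparison, yet the plan would feed 10 such subjects into one side of it, with no concurrent randomised controls during the pilot. Whatever distinguishes pilot from later subjects (calendar time, surgical and physiotherapy experience, patient selection) would be confounded with treatment.

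Three further consequences follow.

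- **Timing.** The last outcome is measured at 14 weeks. If recruitment waits for that result before the sample size is set, at least 14 weeks separate the last pilot surgery from the next one, against a recruitment period of about 6 months.
- **Blinding.** The plan says that "The statistician will be blinded to the subjects group until the statistical analysis is completed". Anyone who can identify the pilot subjects and knows which group was used also knows their allocation. The documents do not say whether the evaluator or statistician could.
- **Sample size.** One group cannot estimate a between-group difference. The pilot can supply only an SD, and the plan gives no target difference to go with it.

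**Working it through.** **Inputs from the documents.** Pilot of 10, all in one group and retained by default; about 30 per group (SAP, Size Sample and Feasibility); simple 1:1 randomisation (protocol sections 2 and 8C); 80% power and 5% significance (SAP). Two-sided testing is assumed, because the plan does not state sidedness.

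**The plan's own figure.** The 30 per group cannot be reproduced, because no effect size or SD is given. It is justified by the size of published studies and by prevalence. At 80% power, 30 per group detects 0.74 SD with the t-test. The normal approximation gives (1.960 + 0.842) × √(2/30) = 0.72 SD.

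**Step 1: can both statements be true?** Under simple 1:1 randomisation, the chance that all 10 fall in one arm is 2 × 0.5¹⁰ = 0.00195, or 0.2%. A pilot that uses the trial's methodology and puts everyone in one group is therefore a contradiction in practice.

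**Step 2: share of the arm that is not randomised, for 60 in total.**

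- The other 50 are randomised 1:1 as stated, giving 25 and 25. The final arms are 35 and 25, and the share is 10/35 = 28.6%. Simple randomisation lets the 25 vary from 18 to 32 (95% range), so the share could be 10/28 = 36% to 10/42 = 24%.
- The final arms are held at 30 and 30. The other 50 must be split 20:30, which is not 1:1, and the share is 10/30 = 33.3%.

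**Step 3: bias and type I error.** Bias = shift × share, where the shift is the systematic difference between pilot and later subjects in SD units. The documents give no value for it, so the range below is an assumption. Type I error is for a two-sided pooled-variance t-test at 5% with no true effect (200,000 simulated trials per cell).

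| Assumed shift (SD) | 25+10 vs 25: bias (SD) | Type I error | 20+10 vs 30: bias (SD) | Type I error | 58+10 vs 58: type I error |
|---|---|---|---|---|---|
| 0 | 0 | 4.95% | 0 | 4.94% | 4.99% |
| 0.25 | 0.07 | 5.7% | 0.08 | 6.1% | 5.5% |
| 0.5 | 0.14 | 7.9% | 0.17 | 9.2% | 6.7% |
| 0.75 | 0.21 | 11.3% | 0.25 | 14.3% | 8.8% |
| 1.0 | 0.29 | 15.7% | 0.33 | 21.4% | 11.7% |

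The last column shows a larger trial, close to the 64 per arm needed for 0.5 SD at 80% power. There the pilot's share is 10/68 = 15%.

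**Step 4: what the pilot can tell the sample-size calculation.** With 10 subjects in one group (9 degrees of freedom), the 95% confidence interval for the SD runs from 0.69 to 1.83 times the estimate. N is proportional to the variance, so it ranges from 0.688² = 0.47 to 1.826² = 3.33 times the calculated value.

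**Step 5: cost of leaving the 10 out.** The detectable difference at 80% power is 0.74 SD for 30 vs 30, 0.81 SD for 25 vs 25 and 0.83 SD for 20 vs 30.

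**The case against.** The wording is rough, and the phrase about the same group directly follows a mention of a group of 10 subjects. It might mean only one pilot cohort, and the shared methodology might mean the same eligibility criteria and measurements. That reading is possible but weaker, because the protocol uses assignment and group elsewhere for allocation to an arm. Even on that reading, the sample-size section does not say that the pilot subjects are randomised, so it needs the same correction.

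The size of the harm is assumed. Pilot and later subjects share the clinic, the recruiting surgeons, the eligibility criteria and the evaluation procedure. The plan also checks baseline homogeneity and allows ANCOVA. These features make shifts of 0.75 to 1.0 SD look extreme, and at 0.25 SD the inflation is slight. They do not restore randomisation.

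The shares depend on about 30 per group, a feasibility figure that the calculation after the pilot may replace. That stands. So does the point that the timing and blinding consequences are conditional: a 4-week outcome would shorten the wait, and an internal pilot could face the same wait. In an internal pilot, however, both arms are recruited in the same period, so calendar time is not tied to treatment.

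The unnamed response variable and missing target difference would remain gaps even with a randomised pilot. They belong here because the same paragraph has to be rewritten.

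**Conclusion.** The concern holds and should be fixed before the trial proceeds. As written, the pilot allocation contradicts the 1:1 randomisation, and by default 10 non-randomised subjects enter the between-group comparison. At about 30 per group they are 29% to 33% of one arm, or 15% at 58 randomised per arm. The contradiction does not depend on any assumed shift, but the amount of bias does. For shifts of 0.25 to 1.0 SD, bias is 0.07 to 0.33 SD and type I error 5.7% to 21.4% across the two 60-subject cases. The result rests on the plain reading that one group means one study arm, and on the protocol and variables not changing after the pilot.

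**What to change.** Replace the sentence that puts the pilot subjects in one group with text to this effect:

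> The first 10 subjects are randomised 1:1 from the trial's allocation list and form an internal pilot. Their data are used only to estimate, with group hidden, the SD of [one named response variable] at [one named time point]. N is computed with the two-sample formula for a between-group difference of [X] on that variable, fixed before pilot data are seen.

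Report N over the confidence interval of the SD, given how imprecise 10 subjects make it. An SD estimated with group hidden is inflated by any treatment effect. With a 5:5 split and a true difference of 0.74 SD, the expected variance is about 1 + (10/36) × 0.74² = 1.15 times the within-group value, so N errs on the large side by about 15%. State this.

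If the one-group pilot has already been run, exclude those 10 from all between-group analyses or replace them with 10 randomised subjects. Adding pilot status as a covariate does not rescue them: it is nested in one arm, so they would no longer contribute to the treatment contrast.

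**Cost.** If the pilot has not been run, randomising it needs no extra patients, although the recalculated N may differ from 60. The paragraph must be rewritten to name the variable, time point and target difference. If it has been run, exclusion raises the detectable difference from 0.74 SD to 0.81 or 0.83 SD. Replacement restores 0.74 SD and takes about one month: 60 subjects in 6 months is 10 per month, assuming even accrual.

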5.2. Dependent variables

The dependent variables of the study are the following:

Range of Mobility (ROM).

In the present study measurements will be made by goniometry of hip joint movement ranges. The goniometry is a technique of measurement of the angles created by the intersection of the longitudinal axes of the bones at the level of the joints.

These are continuous quantitative variables, measured in degrees with a range between 0° and 180°.

- a. ROM in hip flexion.
- b. ROM in hip extension.
- c. ROM in hip abduction.
- d. ROM in hip adduction.
- e. ROM in internal hip rotation.
- f. ROM in external rotation of the hip.

Orthopedic tests

The FAI will be checked through the performance of the Fabere, Fadir and Ober functional tests described below.

- a. **FABERE TEST:** The patient's hip is flexed, abducted and externally rotated by placing the external malleolus on the knee of the contralateral leg. The pelvis is

- stabilized and an overpressure is applied to the inside of the knee. It is positive if the pain in the buttock or groin is reproduced. Test with inter-evaluator reliability in Kappa values (95% CI) of 0.60.
- b. FADDIR TEST: Flexion, adduction and internal rotation test. The supine patient, the evaluator patiently brings the patient's hip up to 100° flexion and adduction while applying internal rotation. It is positive if pain in the groin is reproduced. Test with inter-evaluator reliability in Kappa values of 0.48.
 - c. OBER TEST: Patient in lateral decubitus position. The evaluator flexes the knee that is evaluated at 90° and abducts and extends the hip until it is level with the trunk. The evaluator lets the gravity bring the hip on adduction as possible. Test with inter-evaluator reliability of 0.90.

Variable intensity of pain

The Visual Analogue Scale (VAS) will be used. It is a continuous quantitative variable with a range between 0 and 10.

Evaluation functionality.

The modified Harris Scale will be used to the patient to evaluate the functionality of the hip and its interference in the activities of daily life. The patient will be evaluated with this scale prior to the surgical intervention and 14 weeks after the surgery.

6. STUDY GROUPS.

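### The planned group comparison names no baseline covariate in either branch, and an under-specified normality test decides, outcome by outcome, whether means or ranks are compared

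*Combined protocol and SAP*

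**What the plan says.** All of this is in the Statistical Analysis Plan, under Inferential analysis, unless another place is given.

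- Item a is a "Normal distribution test of Kolmogorov-Smirnov to identify the distribution of the samples".
- Item d covers the comparison of results between groups. If the data pass, "we will use the t-Student test of related samples and one-way ANOVA (when they are normal"). If they fail, the plan uses "Mann-Whitney U test or Wilcoxon W test (when they do not meet the normal").
- ANCOVA appears only in item e: "Chi square test or ANCOVA to analyze the influence of the general characteristics of the sample on the effect of the intervention". Item g adds "Regression analysis using the multiple linear model to study the relationship between sets of variables", with no outcome or covariates named. Neither item depends on the result of item a.
- The descriptive analysis reports "the minimum, maximum, average and standard deviation for the quantitative variables", whatever the normality result. No item names a between-group difference or a confidence interval.
- The continuous outcomes in section 5.2 are six hip ROM measures, pain on the VAS and the modified Harris scale. Of the VAS it says: "It is a continuous quantitative variable with a range between 0 and 10". No mean, SD, share of patients at zero or scoring step is given.
- Section 8, step B, has the pre-surgical value of each of these outcomes recorded before allocation.

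**The concern.** There are two linked weaknesses in item d.

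First, the pre-surgical score is available for every continuous outcome but enters neither branch as a covariate. The paired t-test looks at change within one group and is not a between-group comparison. One-way ANOVA and Mann-Whitney compare the groups without adjustment. In a trial of about 30 per arm, the precision given up matters.

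Second, the test is chosen from the trial data and the rule cannot be carried out as written. It does not say:

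- whether the Kolmogorov-Smirnov p-value is corrected for the estimated mean and SD (Lilliefors) or not;
- whether pooled data, each arm, each visit, change scores or residuals are tested;
- what happens if arms or visits disagree;
- which of the two named tests applies within a branch.

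A rank test also does not compare means. Eight continuous outcomes could therefore be reported on a mixture of scales, with no common effect measure.

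**Working it through.** **1. The plan's own figure.** Around 30 per group is given as feasible, with at least 80% power and p < 0.05, but with no difference or SD, so it cannot be reproduced. Solving backwards (two-sided 0.05 assumed, 1:1): d = (1.960 + 0.842) × √(2/30) = 0.723. This is used below only as a reference effect.

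**2. What a baseline covariate is worth, by formula.** With baseline correlation ρ (assumed), ANCOVA multiplies the outcome variance by 1 − ρ². Power is Φ(0.723/√(1 − ρ²) × √15 − 1.96).

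| ρ | 1 − ρ² | ANCOVA power | Unadjusted power |
|---|---|---|---|
| 0.3 | 0.91 | 83.6% | 80% |
| 0.5 | 0.75 | 89.9% | 80% |
| 0.7 | 0.51 | 97.5% | 80% |

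**3. Separating the normality step from the missing covariate.** This needs an ungated unadjusted test in the comparison. Assumptions: latent normal VAS clipped at 0-10, SD 2.5, correlation 0.5, 30 per arm.

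| Latent means | Ungated t | Gated rule | ANCOVA |
|---|---|---|---|
| 3 vs 1.2 | 75% | 75-76% | 84% |
| 2.5 vs 1 | 58% | 59-60% | 68% |

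The gated rule matches the ungated t-test. The gap to ANCOVA is about 9-10 points.

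A second set used SD 2, a latent effect of 1.4 points, correlation 0.5 and 4,000 runs. The Monte Carlo standard error is about √(0.75 × 0.25/4000) = 0.7 points.

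| Control latent mean | One-way ANOVA | Gated, Lilliefors | Gated, uncorrected K-S | ANCOVA |
|---|---|---|---|---|
| 5 | 76.4% | 76.2% | 76.4% | 86.8% |
| 2 | 70.6% | 70.8% | 71.7% | 80.2% |
| 1 | 65.0% | 67.7% | 68.3% | 73.9% |

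Under heavy flooring the normality step gains a little power over plain ANOVA. ANCOVA's lead over the gated rule then narrows to about 6 points (73.9 − 67.7 = 6.2; 73.9 − 68.3 = 5.6).

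**4. Type I error.** With no true difference (same second set), the gated rule rejected in 4.6-5.2% of trials and ANCOVA in 4.4-4.8%.

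**5. How far the unstated details matter.** Chance that at least one arm of 30 fails the test (SD 2, VAS recorded to 0.1 unless stated, 1,500 runs):

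| Share at zero | Uncorrected K-S | Lilliefors |
|---|---|---|
| 7% | 0% | 11% |
| 23% | 2% | 71% |
| 31% | 16% | 96% |
| 41% | 59% | 99.9% |
| 1%, whole-point scoring | 1.5% | 73% |

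ANOVA and Mann-Whitney disagreed on significance in 1.5-10.5% of trials in the second set. Even if all eight outcomes were truly normal, a correctly calibrated 5% normality test applied once to each would send at least one to ranks with probability 1 − 0.95⁸ = 34%, if the outcomes were independent (an assumption).

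**The case against.** The strongest defence is that the switch does no demonstrated harm. It is written in advance, section 2 keeps the statistician blinded to group until the analysis is complete, and both power and type I error are essentially those of an ungated unadjusted test. That stands. Blinding limits deliberate choice, but it does not fill the gaps in the rule or put the outcomes on one scale.

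A reader might infer three stronger things, which the documents do not support:

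- **That the normality step costs power.** This appears only if the gated rule is compared directly with ANCOVA. Against the ungated t-test there is no loss.
- **That it strips the VAS of baseline adjustment or a confidence interval.** The normal branch names neither, so nothing is removed. Items e and g are not conditional on normality, and means and SDs are reported regardless.
- **That the VAS would usually be diverted to ranks.** This depends on the Kolmogorov-Smirnov variant, the share of patients at zero and the scoring step. The plan states none of them, and under uncorrected p-values the VAS would often stay with means.

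It can also be said that item d might be run on change from baseline, since section 2 speaks of change, and so would use the pre-surgical score. Item d does not say this, and change scores do not match ANCOVA. Their variance factor is 2(1 − ρ), that is 1.4, 1.0 and 0.6 at ρ = 0.3, 0.5 and 0.7, against 0.91, 0.75 and 0.51.

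**Conclusion.** The point holds as a low-cost improvement, not as a threat to validity. Item d names no baseline covariate in either branch, and item a leaves the choice between means and ranks to the data under an incomplete rule. The cost in power comes from the missing covariate: about 9-10 points in the SD 2.5 scenarios, and about 6 to 11 points against the gated rule across the SD 2 scenarios. These figures rest on assumed SDs, an assumed baseline correlation of 0.5, a clipped-normal VAS and 30 per arm. By the formula, the gain at the reference effect runs from about 4 points at ρ = 0.3 to about 17 at ρ = 0.7. The normality step adds no material power loss and no type I error inflation. Its cost is that the test and the quantity compared are not fixed in advance, so outcomes may lack a common effect measure.

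**What to change.** For the continuous outcomes (VAS, modified Harris, each ROM measure), replace item d with one analysis that does not depend on item a:

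- ANCOVA of the 14-week score on group and pre-surgical score, reporting the adjusted mean difference with its 95% CI.
- A rank-based or bootstrap result as a named sensitivity analysis.
- Residuals inspected descriptively, with no switch of method as a result.

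Remove the Kolmogorov-Smirnov test as a deciding step for outcome comparisons. Adopting ANCOVA only in the normal branch would not be enough: with the step kept, outcomes failing it would still go to an unadjusted rank test.

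The cost is SAP wording. The pre-surgical scores are already collected, and ANCOVA is already among the planned methods (item e). No extra visits, patients or measurements are needed.
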